#### Inclusion and Exclusion Criteria

#### **Inclusion Criteria:**

Adult patients (≥16 years of age) admitted for mechanical small bowel obstruction. Example etiologies which should be included:

Adhesions.

Hernias with bowel compromise (incisional/parastomal, ventral, inguinal, femoral, obturator, internal).

Malignancy (primary: lymphoma, carcinoid, GIST, adenocarcinoma/metastatic disease: colon, ovarian, gastric, pancreatic, melanoma and others).

Enteroliths/gallstones/bezoars/foreign bodies

Radiation.

Inflammation (Crohn's disease, mesenteric adenitis, appendicitis, diverticulitis, tuberculosis, actinomycosis, ascariasis).

Congenital (malrotation, duplication cysts).

Trauma (hematomas, ischemic strictures).

#### Exclusion criteria:

Functional small bowel obstruction (dysmotility or adynamic ileus secondary to abdominal operations, peritonitis, trauma or medications).

#### Patient follow-up

The audit is designed so normal patient follow-up pathways can be used to obtain outcome data. No additional visits or changes to normal follow-up should be made. However, local investigators should be proactive in identifying post-diagnosis events (or lack thereof), within the limits of normal follow-up. These may include reviewing the patient notes (paper and electronic) during admission and before discharge to note in-hospital complications, reviewing hospital systems to check for reattendances or re-admissions, and reviewing post-operative radiology reports.

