#### **Primary Objective**

To explore differences in patients, management and outcomes across the entire cohort to identify areas of practice variability resulting in apparent differences in outcome warranting further study. The outcomes that the study will examine are:

- Incidence of small bowel obstruction by etiology.
- Differences in clinical presentation.
- Diagnostic work-up.
- Non-operative management strategies.
- Time to surgery and outcomes.
- Complications related to disease and/or therapies within 60 post-operative days.
- Length of Emergency Department and Hospital stay.
- Re-admission within 6 months for related conditions.

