## Data Collection Instrument 10 - Current episode, Final outcome

Current Episode Outcome	Key Name	Data Type	Values
Postoperative Complication	РОСО	Binary	Yes/No (if one at least)
Broncoaspirative pneumonia	BAP	Binary	Yes/No
New Acute Kidney Insufficiency	NAKI	Binary	Yes/No
New Onset Cardiac Arrhythmia	NOCA	Binary	Yes/No
Deep Vein Thrombosis/Pulmonary Embolism	DVT	Binary	Yes/No
Superficial Surgical Site Infection	SSSI	Binary	Yes/No
Deep Surgical Site Infection	DSSI	Binary	Yes/No
Organ Space Surgical Site Infection	OSSSI	Binary	Yes/No
Anastomotic leak	AL	Binary	Yes/No
Reoperation	RELAP	Binary	Yes/No
Most Severe Complication	MSCO	Chain	Named
Clavien Dindo	CLDI	List	I, II, IIIa, IIIb, IVa, IVb, V
ICU	ICU	Binary	Yes/No
ICU Date of Admission	ICUDOA	Date; time	Date of ICU admission dd/mm/yy hh:mm
ICU Date of Discharge	ICUDOD	Date; time	Date of discharge from ICU dd/mm/yy h:mm
ICU Lenght of Stay	ICULOS	Integer	${\it Number of Days (Integer; calculated from the admission and discharge date)}$
Death	RIP	Binary	Yes/No
Readmission during study period	READ	Binary	Yes/No (if after episode)

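### The outcome form cannot separate no event from not ascertained after discharge, so post-discharge complication and readmission proportions cannot be interpreted safely

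*Protocol*

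**What the plan says.** **Source of outcomes.** The Patient follow-up section states: "The audit is designed so normal patient follow-up pathways can be used to obtain outcome data". It adds: "No additional visits or changes to normal follow-up should be made". Within that limit it makes a positive request: "local investigators should be proactive in identifying post-diagnosis events (or lack thereof), within the limits of normal follow-up". The concrete checks follow as examples: in-hospital notes during the stay and before discharge, then "reviewing hospital systems to check for reattendances or re-admissions, and reviewing post-operative radiology reports". Methods for identifying patients also lists electronic flagging of readmissions, as one of several methods to be chosen according to local circumstances.

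**How outcomes are stored.** By count, 13 of the 18 fields in DCI 10 are Yes/No, including the umbrella item "Postoperative Complication", the named complications, reoperation, death and "Readmission during study period". The other five are the named worst complication, the Clavien-Dindo grade, two ICU dates and ICU length of stay. As printed, the form has no unknown value, date of last information, follow-up status or date of readmission.

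**Missing data.** Missing data and retrospective patient entry recognises missing values, lets sites correct them, and excludes centres with more than 5% missing in mandatory fields. It does not say which fields are mandatory.

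**What the fields must support.** Recurrence within 6 months is a primary research question. Primary Objective lists "Complications related to disease and/or therapies within 60 post-operative days" and related readmission within 6 months. A secondary question asks about complications and treatment failure under non-operative management.

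**The concern.** A proportion of patients with a post-discharge event needs a denominator of patients whose outcome is known. Here the denominator will be everyone with an entry, whether or not anyone looked. Two consequences follow.

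- **Level.** Any unchecked *No* that hides an event pulls the reported proportion down.
- **Contrast.** If the chance of being checked varies by centre or by treatment, groups with the same true risk will show different proportions. The stated purpose of the audit is to find practice variability linked to apparent differences in outcome, so this is the kind of artefact it should be able to rule out. All hospitals performing general surgery may join, without limits on size or throughput, so follow-up habits can be expected to vary.

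This is a matter of data capture, fixed in the protocol. An analysis plan cannot recover it once the database is locked.

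**Working it through.** The protocol states no event rate, detection rate or sample size on this point, so there is no figure of its own to reproduce. The check is a reading of the text plus an illustration.

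**1. Can an unchecked patient be recognised in the data?**
- Patient follow-up asks for active case-finding but makes no specific check compulsory and asks for no record that it was done.
- DCI 10 offers *Yes*, *No* or, implicitly, a blank. DCI 8, which Data completion also counts as follow-up information, covers the course of the index episode and has no outcome-check field.
- The completeness rule penalises a blank if the field is mandatory. It never penalises an unchecked *No*.

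So a blank would reveal an unchecked patient, but the rule discourages blanks, and no field distinguishes the two kinds of *No*.

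**2. Is the framing neutral by treatment?** Partly. The readmission checks in Patient follow-up and in Methods for identifying patients apply to all patients. The complication window is counted from surgery, the umbrella complication item is post-operative, and so is the radiology source. A non-operated patient has no start point for the window and no umbrella item.

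**3. How large could the effect be?** All inputs here are assumptions. Let *p* be the true risk of a post-discharge event, equal in both groups, and *d* the probability that an event is detected, with no false positives.

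Apparent proportion = *p* × *d*; apparent ratio = *d*(operated) ÷ *d*(non-operated), which does not depend on *p*.

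| Detection, operated v non-operated | Apparent proportions at *p* = 10% | Ratio |
|---|---|---|
| 95% v 90% | 9.5% v 9.0% | 0.95/0.90 = 1.06 |
| 95% v 80% | 9.5% v 8.0% | 0.95/0.80 = 1.19 |
| 95% v 70% | 9.5% v 7.0% | 0.95/0.70 = 1.36 |

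The same formula applies to two centres with different follow-up habits.

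**4. Could this look like a finding?** Assume 1000 patients per group and a two-sided 5% test. At 95% v 70% and *p* = 10%, the difference is 0.025 and its standard error is √[(0.095×0.905 + 0.070×0.930)/1000] = 0.0123. That gives z = 2.03, and a chance of nominal significance of Φ(2.03 − 1.96), about 53%. It is 29% at *p* = 5% and 85% at *p* = 20%. At 95% v 90% it is only about 5% to 8% over the same range of *p*.

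**5. In-hospital events.** If a share *h* of all events occurs in hospital and is fully captured, the ratio for all events becomes [*h* + (1−*h*)*d*(operated)] ÷ [*h* + (1−*h*)*d*(non-operated)], which moves towards 1 as *h* rises. The ratios in step 3 therefore apply to post-discharge events only.

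**The case against.** The strongest case against runs as follows.

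- **A Yes/No field can be left blank.** The protocol recognises missing data and sets a completeness standard. This stands: a reader might infer that every patient nobody looked up is entered as *No*, but nothing in the protocol says so. What remains is that such an entry can occur and could not be recognised.
- **Investigators are told to establish events or their absence.** This stands as an instruction that covers all patients. It leaves no trace in the data, so compliance cannot be verified or compared between centres.
- **Lower surveillance of non-operated patients is stated nowhere.** This stands. A reader might conclude that the audit will make non-operative care look safer by a definite amount. The post-operative framing makes the direction plausible, but the readmission checks are neutral by treatment and the documents give nothing from which to compute a size.
- **Use of normal follow-up is a deliberate choice in a non-interventional, hypothesis-generating audit, and no formal treatment comparison is specified.** This stands as a reason not to ask for visits or contacts. It does not excuse the form: the descriptive proportions are affected too, and an artefact can generate a false hypothesis.
- **In-hospital outcomes are well covered.** Largely true: notes are reviewed during admission and before discharge. The point is confined to events after discharge.

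**Conclusion.** The point holds as a limitation of data capture for post-discharge complications and readmission. DCI 10 cannot separate no event from not ascertained, the record checks are examples and not requirements, and the completeness rule discourages a blank but not an unchecked *No*, provided that DCI 10 fields are mandatory, which is not stated. Post-discharge proportions, including 6-month recurrence, may be too low and may differ by centre or treatment for reasons of ascertainment.

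The size is unknown. Under assumed detection and equal true risk, the apparent operated to non-operated ratio runs from 1.06 (95% v 90%) to 1.36 (95% v 70%): negligible if ascertainment is nearly equal, material if it is not. The audit collects nothing that would show which applies. A cheap change to the form and one added instruction would supply it.

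**What to change.** 1. **Patient follow-up:** require one look-up for every patient, operated or not, in the hospital's own records (reattendance, readmission, radiology), after the follow-up window closes. That window must first be settled. Key Study Dates gives 31 July 2024 as 60 days from 1 May 2024, but the interval is 91 days (60 days ends on 30 June). Primary Objective counts 60 days from surgery for complications and 6 months for readmission, and 6 months from 1 May 2024 is 1 November 2024.
2. **DCI 10:** add one field recording that the outcome check was done, with its date, or that the outcome was not ascertainable. Give the post-discharge complication and readmission fields a third value, *not ascertained*.
3. **Missing data and retrospective patient entry:** state that *not ascertained* is a valid entry and does not count as a blank for centre exclusion. Otherwise centres are penalised for using it.
4. **Reporting:** give post-discharge proportions over ascertained patients, with the number ascertained by operated status.

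**Cost:** one record look-up per patient in sources the protocol already names, a few form changes, and no visits or change of care. Readmissions to other hospitals will still be missed, and the report should say so.

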#### Data completion

This research is an observational and non-interventional audit that collects data along the usual course patient pathway. The Data Collection Instrument (DCI) has been designed to reflect common parameters. We envisage that participating clinical Centers will identify a team of 4-5 members; one Consultant (clinical 'lead' of the study), trainee surgeons or data administrators who will undertake the logistical roles as well as co-ordinate data entry.

DCI 2 (patient demographics), DCI 3, 4, 5 (past medical and surgical history) and DCI 8 and 10 (follow-up information) can be completed by any suitably qualified member of the local team. DCI 6 (Current episode emergency details) and F7 (Initial complementary exams) must be completed by or in direct conjunction with an admitting staff surgeon who was present, as DCI 9 (operation details) by a staff surgeon also present itself. It should ideally be completed as close to the end of surgery as feasible, to ensure data accuracy and completeness.

#### Missing data and retrospective patient entry

The online database has been designed to allow sites to securely access an individual patient's data throughout the study period. This means that any missing or erroneous data can be altered by the local investigators whilst the data collection period is ongoing. In order to maximize data completion and emphasize its importance to collaborators, participating Centers with >5% missing data in mandatory fields (i.e. less than 95% data completeness) will be excluded from the study.

The study design means that sites may retrospectively identify eligible patients that were missed primarily and for whom contemporaneous patient and operation data was not entered.

#### Data collection system and information governance

Data will be recorded on a dedicated, secure server running on the REDCap® web application. REDCap® allows for secure upload and storage of data, in compliance with European Union General Data Protection Regulation 2018 (GDPR) and the Health Insurance Portability and Accountability Act of 1996 (HIPAA) legislation.

Registered local investigators will have individual password-protected access to their unit's data entered on to REDCap®. During the running of the audit, only local data will be visible to individual investigators; other sites' data will not be accessible. It is the responsibility of each participating Center to ensure their own records comply with local data governance legislation, GDPR or HIPAA, as applicable.

#### Local approvals

All data collected will measure current practice, with no changes made to normal treatment. As such, this study should be registered as an audit of current practice at each participating Center. It is the responsibility of the local team at each site to ensure that local audit approval (or equivalent) is completed for their Center. Participating Centers will be asked to confirm that they have gained formal approval at their site.

#### **Authorship**

Investigators from each individual site will be included as formal co-investigators in this research, and will be PubMed searchable and citable. The output from this research will be published by the steering group on behalf of a single corporate authorship – e.g "ESTES SnapSBO Group."

#### Publication of data

The report of this audit will be prepared in accordance with guidelines set by the STROBE (strengthening the reporting of observational studies in epidemiology) statement for observational studies8, (appendix C) Data will be published as a pool from all participating units. Subgroup analyses by disease, technique or outcome variables may be presented, but no hospital-level or surgeon-level data will be published whereby an individual patient, unit or surgeon could be identified. If local investigators would like a breakdown of their own unit's data for benchmarking purposes and local presentation/discussion, this can be made available after the end of the study; however, it will not be possible or permissible to de-anonymise patient data stored in REDCap®, in strict compliance with GDPR and HIPAA.

#### Data governance

The ESTES Cohort Studies Committee welcomes the use of the data for further research that benefits patients. Requests can be submitted to the ESTES Cohort Studies Committee. Data sharing is subject to ESTES approval and the appropriate safeguarding as determined by the ESTES. Any future sub-projects should also comply with our policy of a single corporate authorship e.g. "ESTES SnapSBO Group" or similar. However, authors' contributions will be highlighted in accordance with the recommendations for the conduct, reporting, editing, and publication of scholarly work in medical journals.

#### Financial arrangements

This study is undertaken voluntarily by participating institutions under the coordination of the Emergency Surgery Cohort Study Steering Committee. It is not anticipated that participating Centers would bear any costs. Similarly, no financial reimbursement will be made to units or investigators.

# **REDCap® Data Collection Instruments**

## Data Collection Instrument 1 - Patient and Centre Demographics

Hospital Details*	Data	Values
Primary, Secondary or Tertiary Hospital	List	List
Number of Beds	Integer	0 – 3000
Number or UCI beds	Integer	0 – 3000
Emergency Theatre	List	Tick Applicable
Acute Surgical Assessment Unit	Binary	Yes/No
Number of General Surgery Consultants	Integer	1-20
Split on call (Upper + Lower GI available)	Binary	Yes/No
Acute Care Surgery	Binary	Yes/No
Is ERAS practiced in General Surgery?	Binary	Yes/No

\*will be filled once for each center

### Data Collection Instrument 2 - Patient demographics

Demographics	Key Name	Data Type	Values
Country Code	СС	List	List of included countries (chain, number)
Center ID	CID	List	List of study centers (chain, number)
Patient ID	PID	Chain	Country code-Centre ID-patient number (chain, number)
Age (years)	AGE	Integer	Number
Sex	SEX	List	Male, Female
Body Mass Index	ВМІ	Integer	Weight (Kg) Height (Cm) BMI (integer)
Date of Admission	DOA	Date; time	Date of index admission dd/mm/yy hh:mm
Date of Discharge	DOD	Date	Date of discharge from hospital
Length of Stay	LOS	Integer	Number of Days (Integer; calculated from the admission and discharge date)
Cathegory	CAT	List	Ethiology (Adhesions, Bezoar, Gallstone ileus, Hernia (primary/internal/incisional/parastomal), Stenosis (anastomotic, inflammatory/endometriosis), Tumor (primary/carcinomatosis/Radiotherapy), congenital (malrotation)

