### **Secondary Research Questions**

- What is the incidence and etiology of virgin abdomen SBO?
- What is the incidence of early postoperative SBO?
- What is the success rate for non-operative management?
- What is the prevalence of complications and treatment failure in the nonoperative management of SBO?
- Proportion of patients that underwent WSOC challenge, and under what indications?
- What are the Patient Related Outcomes results?

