# Data Collection Instrument 5 - Patient past SBO history

Past SBO history	Key Name	Data Type	Values
Previous SBO	PSBO	Binary	Yes/No
Number SBO Previous Episodes	NOE	Integer	Number
Date Last Episode	DLE	Date	dd/mm/yy
Previous WSOC challenge	PG	Binary	Yes/No
Previous Success Non-operative Treatment	PSCT	Binary	Yes/No
Previous Single Band Addesion	PSBA	Binary	Yes/No
Previous Small Bowel Resection	PSBR	Binary	Yes/No
Previous SBO Etiology	PSBOE	Chain	Previous SBO cause (Adhesions/Primary Hernia/Incisional Hernia/Parastomal Hernia/Bezoar/Radiation enteritis/Primary tumor

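### The visible etiology list (CAT) cannot code every cause named in the inclusion criteria, and it groups radiotherapy under tumor

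*Protocol*

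**What the plan says.** The Protocol's Primary Objective opens its list of outcomes with "Incidence of small bowel obstruction by etiology". The Secondary Research Questions ask "What is the incidence and etiology of virgin abdomen SBO". Both need a recorded cause for each patient's current episode.

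The Inclusion Criteria give eight groups under the words "Example etiologies which should be included". Among them are "Malignancy (primary: lymphoma, carcinoid, GIST, adenocarcinoma/metastatic disease: colon, ovarian, gastric, pancreatic, melanoma and others", radiation as an entry of its own, "Enteroliths/gallstones/bezoars/foreign bodies" and "Trauma (hematomas, ischemic strictures". The remaining groups are adhesions, hernias, inflammation and congenital causes.

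Data Collection Instrument 2 holds the field CAT, of type List. Seven top-level values are visible: adhesions, hernia, bezoar, gallstone ileus, stenosis, tumor and congenital. Some carry sub-values in brackets. Stenosis is divided into anastomotic and inflammatory/endometriosis, congenital names malrotation only, and tumor reads "Tumor (primary/carcinomatosis/Radiotherapy".

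Data Collection Instrument 5 has a separate field, PSBOE, for the cause of a previous episode. It names "Radiation enteritis" alongside primary tumor. Its type is Chain, not List.

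**The concern.** A field that feeds the first listed outcome should have a place for every cause that the same document tells sites to enrol. If it does not, the person entering the record must leave the field empty or choose the nearest wrong value. Neither can be put right at analysis, because the true cause was never captured. For that reason an analysis plan could not repair the gap.

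The virgin-abdomen question is exposed as well. The Definitions section decides membership of that group by absence of prior surgery alone, so unoperated patients with earlier radiotherapy or peritoneal inflammation stay inside it. Radiation and non-stenotic inflammation are among the causes that the visible list handles least well.

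There may also be pressure toward a wrong code. The section on missing data excludes centers with more than 5% missing in mandatory fields. If CAT is mandatory, which the Protocol does not state, a site with an uncodable case has a reason to pick something rather than leave a blank.

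**Working it through.** The Protocol states no figure to reproduce here. The check is a comparison of the eight inclusion groups with the visible CAT values.

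| Inclusion group | Visible CAT value | Match |
|---|---|---|
| Adhesions | Adhesions | Yes |
| Hernias | Hernia, with coarser subtypes | Yes, at top level |
| Malignancy | Tumor; metastatic disease appears only as carcinomatosis | Yes, at top level |
| Intraluminal causes (4 named) | Bezoar and gallstone ileus | Partial: 2 of 4; no foreign body or enterolith |
| Inflammation (7 named) | Only as a type of stenosis | Partial: appendicitis or mesenteric adenitis without stenosis has no clear value |
| Congenital (2 named) | Malrotation | Partial: 1 of 2; no duplication cyst |
| Radiation | Sub-value of tumor | Grouped under a different cause |
| Trauma (2 named) | None | No value of its own; ischemic strictures could go under stenosis, hematomas could not |

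Count: 3 matched + 3 partial + 1 grouped elsewhere + 1 without a value = 8 groups. No other or unknown value is visible to take the remainder.

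**Effect on the tumor share.** Let T be the true share of cases due to tumor and R the share due to radiation. If only the top level is reported, the tumor share reads T + R. The absolute excess is R and the relative excess is R/T. If the sub-level is stored and reported, the excess is zero. The Protocol gives neither T nor R, and it does not say which level is stored or reported.

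Purely to show the form, assume T = 10% and R = 1% to 4%. Top-level reporting would then give 10% + 1% = 11% up to 10% + 4% = 14%, a relative excess of 1/10 = 10% up to 4/10 = 40%. These inputs have no basis in the Protocol, and another T gives another ratio.

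**Effect of the missing values.** This part does not depend on the reporting level. Its size is the combined share of traumatic hematoma, foreign body or enterolith, duplication cyst, non-stenotic inflammation and unlisted causes. The Protocol gives none of these shares.

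**Whether other fields fill the gap.** The radiotherapy flag RTP in Data Collection Instrument 3 records history, not the cause of this episode. The Crohn's disease, endometriosis and abdominal malignancy fields there share that limit. The free-text CT diagnosis CTE in Data Collection Instrument 7 exists only for patients with a CT diagnosis and is not the final etiology. These fields could prompt queries on some records, but they do not replace a final code.

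**The case against.** Several points on the other side are sound.

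- *Radiotherapy is a named sub-value.* It is written in the same way as the hernia subtypes, which suggests that sub-levels are meant to be recorded. A radiation case would then be retrievable. A reader might infer that the tumor share is certain to be inflated; the text supports this only if results are reported at the top level, and that choice may sit in an analysis plan that is not shown.
- *PSBOE does not prove a contradiction.* A reader might infer that one cause is coded in two ways in one database. But PSBOE is a Chain field, a type that the forms also use for entries that look like free text, such as surgical technique and CT diagnosis, and it concerns a previous episode. Both fields can tell radiation from primary tumor; only the grouping differs.
- *The inclusion list consists of examples.* CAT therefore need not copy it item by item. It should still be able to code each group that the list says should be included.
- *Not every trauma or inflammation case is uncodable.* Ischemic strictures can go under stenosis, and inflammatory is a visible type of stenosis.
- *The cell may be incomplete.* The bracket opened at the start of the CAT values never closes, so a later value, possibly an other category, may have been lost when the text was read. The claim about missing values carries this caveat. The radiotherapy grouping lies wholly within the visible text and does not.

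What remains is a gap in coverage, not proof that the outcome as a whole would be misclassified.

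**Conclusion.** The point holds as a real but probably small coverage gap in the field behind the first listed outcome. On the visible text, one of the eight inclusion groups has no value of its own, three are covered only in part, and one is grouped under a different cause. Eligible cases with the uncovered causes would be blank or wrongly coded. The size cannot be computed, because the Protocol gives no etiology shares; calling it small is a judgement.

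Two assumptions matter. The missing-value part assumes that the visible CAT list is complete. The effect on the tumor share assumes top-level reporting. The documents do not support the broader inference that incidence by etiology is misclassified throughout.

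**What to change.** Revise CAT so that every group in the Inclusion Criteria can be coded; word-for-word identity is not needed. Make radiation a top-level category separate from tumor. Add trauma, foreign body/enterolith and inflammation without stenosis, let the congenital category take duplication cysts, and add other (specify) and unknown. If the live form already has some of these values beyond the visible text, only the remainder needs adding. Using the same categories for PSBOE would help comparison between previous and current episodes, but is optional.

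The cost is a small edit to one pick list, with no new data item. If records have already been entered, sites would need a query on blank CAT values and on cases that may have been placed in a near category. The Protocol lets sites amend their entries while data collection is ongoing, so the query should go out within that period.
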